Figure 7. Communication Between Scanner and Display	25
Figure 8. General Schematic of Scanner Operations	27
Figure 9. Steps to Create the TIFF FOV Image.....	31

ABBREVIATIONS AND TERMS

Abbreviation	Term
AE	Adverse Event
ANA	Average Negative Agreement
APA	Average Positive Agreement
CAP	College of American Pathologists
CI	Confidence Interval
CFR	Code of Federal Regulations
CMOS	Complementary Metal-Oxide Semiconductor
CRF	Case Report Form
CRO	Contract Research Organization
eCRF	Electronic case report form
EDC	Electronic Data Capture
EP	Enrolling Pathologist
FDA	Food and Drug Administration
FFPE	Formalin-Fixed Paraffin Embedded
FOV	Field of View
GCP	Good Clinical Practice
H&E	Hematoxylin and Eosin
ICH	International Conference on Harmonisation
ID	Identifier
IRB	Institutional Review Board
IT	Information Technology
LED	Light Emitting Diode
NA	Numerical Aperture
NPA	Negative Percent Agreement
PHI	Protected Health Information
PI	Principal Investigator
PIPS	Philips IntelliSite Pathology Solution
PPA	Positive Percent Agreement
R1	Reading 1
R2	Reading 2
R3	Reading 3
RP	Reader Pathologist

Abbreviation	Term
SC	Study Coordinator
TIFF	Tag Image File Format
US	United States
USB	Universal Serial Bus
VEP	Verifying Enrolling Pathologist
WSI	Whole Slide Imaging

1. PROTOCOL SUMMARY

1.1 Synopsis

TITLE OF TRIAL NanoZoomer S360MD Digital Slide Scanner System Clinical Validation Protocol for Feature Detection Precision
TRIAL SITE(S) Three (3) sites in the United States (US) and possibly Canada. 1. Ohio State University Wexner Medical Center, PI ([name]) 2. Cleveland Clinic Foundation PI ([name], [name]) 3. Washington University Medical Center, PI ([name]) Detection of histologic feature by 3 reader pathologist for each of 3 substudies Case screening and enrollment to use 1 pathologist to screen and enroll cases and 1 verifying pathologist to confirm case eligibility for enrollment
OBJECTIVES Primary Objective: To evaluate the repeatability and reproducibility of detection of histological features using WSI under following 3 sub-studies: 1. Scans within scanner (Intra-scanner precision substudy), 2. Scanners within a site (Inter-scanner precision substudy), and 3. Scanners between sites (Inter-site precision substudy).
ENDPOINTS The endpoints are specific to each sub-study: 
Overall percent agreement between scans (e.g. between scan1 and scan2, or scan1 and scan3, or scan2 and scan3) within a given scanner (Intra-scanner precision)Overall percent agreement between scanners (Inter-scanner precision)Overall percent agreement between sites (Inter-Site precision)
METHODOLOGY Pathologists will be asked to identify a particular histological feature present in a field of view (FOV) image from the WSI image of a single slide. The slides will be selected and will contain one particular screened and enrolled feature from an organ at a particular magnification as listed in Table 1 . From these images, a TIFF image demarking the feature(s) of interest in a particular FOV will be created representing only a small discrete region of the entire slide consistent with field viewed at 10, 20 or 40x. The TIFF images will then be presented to the pathologist who will be asked to identify the feature(s) in the FOV from a list of possible multiple-choice features. Additionally, “sham” images of known features will be inserted into the reading deck to reduce recall bias, but will not be included in the analysis. Then, depending on the sub-study, the slide will be scanned three times on 1 scanner, or once on 3 different scanners. For the intra-scanner substudy, three scanners will be used, the slides will be divided equally among the scanners and scanned 3 times per assigned scanner for a given reading pathologist, and each of 3 pathologists will identify the features across 3 reading sessions separated by a 2-week wash out period between readings. For the inter-scanner substudy, 3 scanners will be used, the slides will be scanned once per scanner and 3 separate

pathologists will identify the features.

For the inter-site substudy, 3 sites, each with one scanner, will be used. The set of enrolled slides will be sent to site 2 and 3. These slides will be scanned once per scanner and 1 separate pathologist per site will identify the features in this substudy.

NUMBER OF SLIDES

A total of 21 features, 7 features at each of 3 viewing magnifications (10x, 20x, 40x), 3 organs within each feature, and 6 slides within each feature-organ combination resulting in 378 FOVs. There will be a total of 9 sham features, 3 at each of 3 viewing magnifications (10x, 20x, 40x), and 18 slides for each sham feature, within each sham features-magnification combination resulting in 162 FOVs sham slides.. The slides will be selected in consecutive order starting with slides at least 1 year old. An enrolling pathologist will screen and enroll the slides per the inclusion and exclusion criteria, which will be verified by a separate validation enrolling pathologist.

MAIN CRITERIA FOR INCLUSION / EXCLUSION

- Inclusion criteria:
 - Slides are selected from cases in a consecutive manner starting with cases at least one (1) year old since accessioning
 - Slide is a glass cover-slipped surgical pathology slide of human tissue
 - Slide stained with H&E or other stains
 - Slide has one of the designated primary feature in the FOV, which is readily observable in its natural environment although the slide may also have one or more secondary features from the same magnification group in the same FOV
 - Slide is available in the archives for use, or purchased commercially, is not damaged, has tissue on the slide which is still in good condition, has a stain that is not faded and otherwise passes all quality checks
- Exclusion criteria:
 - Slide is unable to be scanned, contains damaged tissue or has indelible markings
 - Slide comes from an active (less than 1 year old) case
 - Slide is from a patient who already has a slide enrolled in the study, only 1 slide per patient to be enrolled

DEVICE DESCRIPTION

Hamamatsu S360MD NanoZoomer Slide Scanner Digital Pathology System (NanoZoomer) is an automated digital slide creation, viewing, and management system. The Hamamatsu NanoZoomer S360MD Digital Slide Scanner creates diagnostic quality WSI digital images of glass slides containing formalin-fixed paraffin embedded (FFPE) tissue. Each image typically contains billions of image pixels, creating a digital image of the tissue on the original glass slide. The NanoZoomer captures digital images of entire slides for duplication, annotation, storage, retrieval, image sharing and viewing to permit the pathologist to make a primary diagnosis without needing to view those glass slides through a light microscope.

STATISTICAL METHODS

1. Intra Scanner Substudy

Each of 3 scanners will scan one-third of the slides 3 times for each reader (in such a way that at the end of this sub-study, all 378 study slides will be scanned by each scanner three times and all 378 slides will be evaluated by each reader, details are given in section 8.1). Three reading pathologist will evaluate all scanned slides across 3 reading sessions. In addition to 378 study FOVs selected, 162 “sham” FOVs of the different features will be selected per the same inclusion and exclusion selection criteria and inserted into the reading of slides battery to minimize or avoid bias by the reading pathologist, but the results of sham readings will not be included in any analysis.

The number of comparison pairs is calculated based on 3 readers where for each reader there are 3 pairwise comparisons, namely scan1 vs. scan2, scan1 vs. scan3, and scan2 vs. scan3, which results in 3 readers x 126 pairs per comparison x 3 pairwise comparisons =1134.

To evaluate Intra-Scanner precision for scanner A, three single 2x2 tables can be constructed for pairwise comparisons within scanner A and Reader1. The result of reading for each slide is “Yes” or “No” if the feature was detected correctly or not. Each feature shall be considered as of equal importance as the next feature; thus, the results of all features will be pooled.

Nine (9) 2x2 tables will be pooled within scanner A and across 3 readers to create a table for $scan_{ki}$ verses $scan_{kj}$ for Readers k ($k=1,2,3$) and $i \neq j$ (for $i=1,2,3$ and $j>i$). Then the Agreement Rate for each Scanner = $(a^1+d^1)/1134$ and 95% confidence interval (CI) will be estimated.

The overall Intra-Scanner Agreement Rate will be calculated by averaging all pairwise comparisons results over all 378 slides with selected features enrolled and all 3 pathologists. The overall number is 378 slides with selected features x 3 scanners x 3 readers = 3402. To preserve the correlation structure of multiple readings of the same feature and possibly multiple features on an FOV, the bootstrap method will be used to derive a two-sided 95% CI for the overall agreement rate. An FOV will be the bootstrap re-sampling unit.

The study acceptance criterion is 85% on the lower limit of the 95% CI for the overall agreement rate.

2. Inter Scanner Substudy

All same set of 378 study slides already enrolled with selected features and FOVs will be scanned once on each of 3 scanners all at the same site. In addition, the same 162 “sham” slides will be used in the inter-scanner study.

Three separate reading sessions will be performed by each of 3 new pathologists (different from pathologists used in Intra-Scanner Sub-study 1) with a washout period of at least two weeks between sessions. The 378 study slides that will be read during a reading session will be randomly selected without replacement from the slides scanned from 3 different scanners (details given in section 8.2). Per reading session, 54 different sham slides, 18 sham cards from each of 3 magnification FOVs will be added such that all 162 sham slides will be read by each reading pathologist. The sham slides are not used in determining precision.

To evaluate the inter-scanner precision, we need to estimate precision for 3 pairwise comparisons, namely scanner A vs. scanner B, scanner A vs. scanner C, and scanner B vs. scanner C. For pairwise comparison (scanner A vs. scanner B), three (3) 2x2 tables can be constructed for each of 3 readers. A 2x2 table can be created by pooling above three 2x2 tables for estimating agreement rate between scanner A, scanner B and scanner 3. The overall Inter-Scanner Agreement Rate will be calculated similar to one in Intra-Scanner study.

The study acceptance criterion is 85% on the lower limit of the 95% CI for the overall agreement rate.

3. Inter Site Substudy

In this study, there will be 3 sites and a different reading pathologist at each site, using 3 pathologists different from substudy 1 and 2. For inter-site study, the same set of 378 study slides will be scanned once at each site and each of the 3 reading pathologists will have only one reading session in which all slides scanned at their site will be read. The order in which the slides will be read at each site will be randomly ordered. No “sham” slides will be used.

The overall Inter-site Agreement Rate will be calculated similar to one in Intra-Scanner study.

The study acceptance criterion is 85% on the lower limit of the 95% CI for the overall agreement rate.

1.2 Schema

[figure not shown]

Figure 1. Study Schema

2. INTRODUCTION

2.1 Background

Whole Slide Imaging (WSI) has emerged as an alternative way to view pathology slides instead of the conventional method of viewing slides of tissue under a traditional light microscope used for primary diagnosis. There is growing adoption of the use of WSI for primary diagnosis in many countries (1-4). WSI is particularly advantageous for remote consultation where pathologists are not available over vast geographical regions, and for easier archiving of images of slide material that may have longer shelf life in digital form. In the United States (US), WSI is increasingly used for teaching, archiving, consultation, and research. Furthermore, the College of American Pathologists (CAP) has published recommendations to pathologists who wish to validate WSI in their clinical practices (5).

However, quite recently, in a clearance letter (6) and device summary (7), the Food and Drug Administration (FDA) has announced the approval of the Philips IntelliSite Pathology Solution (PIPS) for use of WSI for primary diagnosis, specifically permitting WSI for in-vitro diagnostic use as an aid to the pathologist to review and interpret digital images of surgical pathology slides prepared from formalin-

fixed paraffin embedded (FFPE) tissue, but not intended for use with frozen section, cytology, or non-FFPE hematopathology specimens.

Thus, with the clearance of the PIPS device for primary diagnosis, this allows the PIPS system to properly serve as a predicate device for any future 510(k) submissions for WSI systems seeking clearance for intended use of WSI, and, further, the FDA has indicated that a clinical study to prove repeatability and reproducibility of histological feature detection by viewing WSI images is a “special control” required to acquire that clearance.

Presently, Hamamatsu is developing a digital slide scanner system, the NanoZoomer S360MD Digital Slide Scanner System (NanoZoomer), for the same intended use as the PIPS system. Thus, Hamamatsu will make the submission in the form of a 510(k) premarket notification with understanding that the PIPS device is the predicate device, will accordingly adhere to the special controls that are established, and, in the spirit of “substantial equivalence,” will follow similar study designs to test the Hamamatsu system. Further, Hamamatsu intends to use the data from this non-significant risk study for the 510(k) submission to clear its NanoZoomer system for the same intended use.

2.2 Rationale

In order for pathologists to make a primary diagnosis using a WSI image they need to be able to both detect and interpret various microscopic morphological features in the pathology digital image. For example, pathologists frequently rely on finding mitotic figures and/or necrosis in tumors to help them make a diagnosis of malignancy. This ability may vary among pathologists (e.g., skill increases with experience), between cases (e.g., simple versus complicated biological entities), and with diagnostic image quality (e.g., may be easier with higher resolution). In general, the reproducibility of feature recognition and related accuracy of diagnosis in the published literature is poor (15-23).

This study is being conducted in order to meet the regulatory requirements for feature detection of the Hamamatsu NanoZoomer S360 MD system. In particular, the study will determine how well a pathologist can repeatedly identify key histologic features present in a field of view” (FOV) of a region of the histological slide at 3 different magnification levels. The reader pathologist will read multiple TIFF images of these FOVs from multiple scans across the study.

There are three sub-studies evaluating the within and between scanner precision as well as the between site precision, namely:

1. Intra-Scanner Precision Substudy
2. Inter-Scanner Precision Substudy
3. Inter-Site Precision Substudy

Recently, the FDA has announced the approval of the PIPS for use of WSI for primary diagnosis in a clearance letter (6) and device summary (7), which included more information on the design, conduct, and acceptance criteria for the reproducibility and repeatability study of histologic features used to acquire clearance.

In light of the clearance of the Philips system, Hamamatsu recognizes that the PIPS device is the predicate device for clearance of its WSI system for that intended use, that the feature detection precision study is required as a special control, and, in the spirit of “substantial equivalence,” is using this mentioned

information as guidance in how to design, execute and assess repeatability and reproducibility of the NanoZoomer 360MD system.

In two PowerPoint presentations (8, 9) the FDA has defined that manufacturers seeking clearance of their WSI devices for primary diagnosis in surgical pathology must demonstrate that a pathologist using WSI technology can achieve reproducible detection of histologic features. Those presentations provide only some general guidelines regarding the number of features, organ systems, magnification at which feature is detected, and number of scanners and readers. The additional information from the clearance letter and device summary provides deeper insight into the approval process for which substantial equivalence must be demonstrated

In the FDA information, three sub-studies for intra-scanner, inter-scanner, and inter-site repeatability and reproducibility are described (7) and further information is also provided related to the number of sites, scanners, pathologists, features, organs, magnifications, and examination of a limited FOV for detection of features. In addition, the precision of feature detection is mentioned as a special control for WSI clearance (6).

Outside of the FDA released information, further information is available from ClinicalTrials.gov study registration website (10) as well as presentations made by Philips (11). In May 2017, at the Pathology Informatics Summit in Pittsburgh, PA (12), Philips presented their features study with the features selected, the different magnifications, multiple choice selection of the expected feature, inclusion and exclusion criteria for slides with the desired feature, the limited FOV used for feature detection, and the acceptance criterion. The acceptance criterion was established as the lower limit of the 95% confidence interval greater than 85% for overall agreement.

2.3 Risk/Benefit

Since this is a retrospective examination of features from cases already available and archived at the site and that will be de-identified, and since there is no determination of diagnosis in this study, there is no apparent risk or benefit to the patient whose case is being used for the study.

3. OBJECTIVES AND ENDPOINTS

3.1 Primary Objective

To evaluate the repeatability and reproducibility of detection of histological features when using WSI under following sub-studies:

1. Scans within scanner (Intra-scanner Precision),
2. Scanners within site (Inter-scanner Precision), and
3. Scans between Sites (Inter-site Precision).

3.2 Primary Endpoint

The endpoints are specific to each sub-study:

1. Overall percent agreement between scans within a given scanner (Intra-scanner precision)
2. Overall percent agreement between scanners (Inter-scanner precision)
3. Overall percent agreement for scans between sites (Inter-Site precision)

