Legend: Eosinophil granules is the enrolled feature for this FOV. The magnification is 40x. The Reader Pathologist, however, may select any and all of the 10 multiple choices features listed, if detected in the FOV. The primary feature is present in the FOV, but other secondary features may also be in the same FOV.

[figure not shown]

Figure 6. Example CRF for Feature Detection at 40x Magnification

For the within scanner precision substudy, the same images will be acquired by scanning three times on the same scanner, allowing the scanner to cool down at least six hours between each iteration. For the between scanner precision substudy, the same images will be acquired by scanning on three different scanners. For the between site precision substudy, the same slides will be sent to the other sites. Fresh images will be acquired by scanning on different scanners at each of three different sites. Fresh TIFF FOV images will be created at the other sites. The pathologist at each of the sites shall read their own site's FOVs one time. The precision of these repeated readings from three different pathologists will be calculated and measured against a pre-established target of 85%. The lower limit of the two-sided, 95% confidence interval of the overall precision will be compared to 85%. For the between site precision, one pathologist from each site will be included (three pathologists overall). Different pathologists will be used for each of the 3 substudies.

The features to be tested are given in [Table 1](#) and the organs in which the features may be found are given in [Table 2](#). Overall there will be 21 features evaluated, 7 features for each of 3 viewing magnifications (10x, 20x and 40x). In addition a total of 9 sham features in the study, using 3 separate sham features for each of the 3 viewing magnifications.

Table 1: Features and Magnifications for Viewing

Feature # / Magnification	10x	20x	40x
Rationale	Tissue level	Cellular level	Subcellular level
1	Small artery	Reed Sternberg cell	Cilia
2	Psammoma body	Polymorph neutrophil	Eosinophil with granules
3	Keratin pearl	Plasma cell	Mitotic Figure
4	Granuloma	Goblet cell	Infiltrating or metastatic lobular carcinoma
5	Adipocyte	Macrophage	Osteoid Matrix
6	Gland	Foreign body giant cell	Intercellular Bridges
7	Necrosis	Clear cell (of Renal Cell Carcinoma)	Hemosiderin
8	Cartilage	Myxoid stroma	Intranuclear inclusion
9	Duct	Muscle cell	Melanin pigment
10	Nerve	Calcification	Crystals

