Scanner C	a^3+d^3	1134	(a^3+d^3)/1134	
Overall	a^*+d^*	3402	(a^*+d^*)/3402	

The overall Intra-Scanner agreement rate will be calculated by averaging all pairwise comparisons results over all 378 slides with selected study features enrolled and all three pathologists. The overall number is 378 slides with selected features x 3 scanners x 3 readers = 3402. To preserve the correlation structure of multiple readings of the same feature and possibly multiple features on an FOV, the bootstrap method will be used to derive a two-sided 95% CI for the overall agreement rate. An FOV will be the bootstrap re-sampling unit.

Above analyses will be performed for primary feature.

The study acceptance criterion is 85%. The lower limit of the 95% CI for the overall agreement rate will be compared to 85% and if the lower limit is greater than 85%, then the study will have demonstrated intra-scanner precision.

In addition to the overall agreement given in [Table 9](#), overall average positive agreement (APA) and overall average negative agreement (ANA) will be provided with their corresponding two-sided 95% CIs.

In [Table 8](#), the percent agreement of scan i with scan j for a positive result is called positive percent agreement (PPA) and is defined as

$$PPA = a^1/(a^1+c^1)$$

The percent agreement of scan i with scan j for a negative result is called negative percent agreement (NPA) and is defined as

$$NPA = d^1/(b^1+d^1)$$

When obtaining PPA or NPA, one cannot assume either scan i or scan j is the reference. Thus, it is suggested that a reasonable summary of positive agreement between two scans is an average of the two PPAs, and a reasonable summary of negative agreement is an average of the two NPAs. These averages should be weighted to reflect the different marginal totals that are used when scan i or scan j is used as the reference. Clinical and Laboratory Standards Institute (28) defines APA and ANA as follows:

$$APA = 2 a^1/(2a^1+b^1+c^1)$$

$$ANA = 2 d^1/(c^1+b^1+2d^1)$$

Table 10 provides the overall APA and overall ANA rates with corresponding 2-sided, 95% CIs by pooling all pairwise comparisons over the three scanners.

Table 10: Intra-Scanner Overall APA and Overall ANA Rates					
	Number of Pairwise Agreement	APA Agreement Rate		ANA Agreement Rate	
		%	95% CI	%	95% CI
Overall	a^*+d^*	$2a^*/(2a^*+b^*+c^*)$		$2d^*/(c^*+b^*+2d^*)$	

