### **2.2 Primary Endpoint**

The endpoints are specific to each sub-study:

[figure not shown]
1. Overall percent positive agreement between scans within a given scanner (Intra-scanner precision)
2. Overall percent positive agreement between scanners (Inter-scanner precision)
3. Overall percent positive agreement for scans between sites (Inter-Site precision)

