**Figure 1: Example CRF for Feature Detection at 40x Magnification**

### **3.1 Required Number of Slides**

The required number of slides is based upon the previously conducted study for the PIPS system. In all three sub-studies, the precision will be based on three reading pathologists' assessments and identification of specific histologic features that are observed in TIFF images of FOVs containing a primary feature.

In two PowerPoint presentations (19) (20) the FDA has stated that manufacturers seeking clearance of their WSI devices for primary diagnosis in surgical pathology must demonstrate that a pathologist using WSI technology can achieve reproducible detection of histologic features. Those presentations provide only some general guidelines regarding the number of features, organ systems, magnification at which feature is detected, and number of scanners and readers. The additional information from the clearance letter and device summary provides deeper insight into the approval process for which substantial equivalence must be demonstrated.

In the FDA information, three sub-studies for intra-scanner, inter-scanner, and inter-site repeatability and reproducibility are described (21) and further information is also provided related to the number of sites, scanners, pathologists, features, organs, magnifications, and examination of a limited FOV for detection of features. In addition, the precision of feature detection is mentioned as a special control for WSI clearance. (2)

Outside of the FDA released information, further information is available from ClinicalTrials.gov study registration website (22) as well as presentations made by Philips, (23) in May 2017, at the Pathology Informatics Summit in Pittsburgh, PA. (24) Philips presented their features study with the features selected, the different magnifications, multiple choice selections of the expected feature, inclusion and exclusion criteria for slides with the desired feature, the limited FOV used for feature detection, and the acceptance criterion. According to the presentation, the acceptance criterion was established as the lower limit of the 95% confidence interval greater than 85% for overall agreement. Additional discussions with FDA clarified that the acceptance criterion for the current study was the lower limit of the 95% confidence interval for Positive Agreement.

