**Table 15: Agreement Table for Scanner A Across all Readers**

		Feature X is correctly identified in Iteration $j$		
		Yes	No	
Feature X is correctly identified in Iteration $i$	Yes	a 	b 	a  +b 
	No	c 	d 	c  +d 
		a  +c 	b  +d 	1134

Then the Percent Positive Agreement (PPA) can be estimated as  $a^1/1134$  for  $i = 1$  to 3, corresponding to Scanner A, Scanner B and Scanner C. Similarly, the results across all three scanners can be summed to obtain the overall PPA (see Table 16).

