The study's acceptance criterion for percent positive agreement is 85%. The lower limit of the 95% CI for the percent positive agreement will be compared to 85%. If the lower limit is greater than 85%, then the study will have demonstrated intra-scanner precision.

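### The protocol applies the 85% rule to overall agreement and the SAP applies it to positive agreement, so the same data can pass one and fail the other

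*Protocol*

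**What the plan says.** **Protocol.** Section 3.2 gives the intra-scanner endpoint as "Overall percent agreement between scans within a given scanner (Intra-scanner precision"), with parallel wording for scanners and sites. Section 8.1.2 estimates it as (a+d)/N and states: "The lower limit of the 95% CI for the overall agreement rate will be compared to 85" per cent. The synopsis and sections 8.2 and 8.3 repeat this rule. Section 4 uses a third term: "The lower limit of the two-sided, 95% confidence interval of the overall precision will be compared to 85" per cent.

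**SAP.** Section 2.2 gives "Overall percent positive agreement between scans within a given scanner (Intra-scanner precision"). Section 6.4.1 estimates it as a/N and states: "The lower limit of the 95% CI for the percent positive agreement will be compared to 85" per cent. Sections 6.5.1 and 6.6.1 do the same. Sections 6.4.2, 6.5.2 and 6.6.2 keep overall agreement as an additional estimate with an interval and no threshold.

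**Reason for the difference.** SAP 3.1 first reports the predicate device's criterion, 85% on overall agreement, which protocol 2.2 also cites. It then says: "Additional discussions with FDA clarified that the acceptance criterion for the current study was the lower limit" of the interval for positive agreement. It does not restate the 85% there, and gives no formula.

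**Terms.** In protocol 8.1.2, "the percent agreement of scan i with scan j for a positive result is called positive percent agreement (PPA) and is defined as" a/(a+c), and average positive agreement (APA) is 2a/(2a+b+c). In SAP 6.4.1, "Then the Percent Positive Agreement (PPA) can be estimated as" a/N. One name carries two formulas.

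**The concern.** Every sub-study has two primary endpoints and two pass rules. In both documents a reading is Yes when the primary feature was detected correctly. Cell d therefore counts pairs in which the feature was missed both times. The protocol rule credits those pairs as agreement and the SAP rule does not. A scanner on which the same features are missed every time counts as precise under the protocol.

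The data are meant to support a 510(k) submission. If the SAP rule failed, the protocol would offer an easier one to fall back on. The protocol's revision history names no change of endpoint (revision 2.0 mentions only a general clarification of statistical methods), and neither document says which takes precedence.

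**Working it through.** **Denominators (from the documents).** 21 features × 3 organs × 6 FOVs = 378 FOVs. Intra-scanner: 3 readers × 126 FOVs × 3 pairs = 1134 per scanner; × 3 scanners = 3402. Inter-site: 378 × 3 pairs = 1134. These reproduce protocol Tables 9 and 17 and SAP Table 16.

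**Ordering of the rules.** (a+d)/N − a/N = d/N ≥ 0. This holds in every bootstrap resample, so on the same resamples the SAP lower limit cannot exceed the protocol lower limit.

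**Worked example (assumed counts).** With 3 readers and 3 reads each, an FOV contributes 9 pairs. Suppose 38 FOVs are always missed, 30 are missed on one of three reads by every reader, and 310 are always detected.

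- d = 38 × 9 = 342
- a = 310 × 9 + 30 × 3 × 1 = 2880
- b+c = 30 × 3 × 2 = 180; total 3402
- Overall agreement = 3222/3402 = 94.7%, bootstrap 95% CI 92.8 to 96.5%: pass
- a/N = 2880/3402 = 84.7%, CI 81.2 to 87.9%: fail
- APA = 5760/5940 = 97.0%, CI 95.9 to 98.0%

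The bootstrap used 20,000 resamples of FOVs within the three sets of 126. A hand check treats the 378 per-FOV rates as independent:

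- a/N: SE = √[(313.33/378 − 0.8466²)/378] = 0.0172, lower limit 0.8466 − 1.96 × 0.0172 = 81.3%
- Overall agreement: SE = √[(351.33/378 − 0.9471²)/378] = 0.0093, lower limit 0.9471 − 1.96 × 0.0093 = 92.9%

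If the discordant pairs split evenly (c = 90), the protocol's PPA is 2880/2970 = 97.0%. A rule of positive agreement above 85% would then pass or fail according to whose formula is used.

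**Simulation (assumed model).** Detection probability is logit-normal across the 378 FOVs with SD 1, 1.5 or 2 and no reader effect; 2000 trials per setting, 800 FOV resamples each. Entries are for SD 1 / 1.5 / 2.

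| Sub-study | True a/N | Protocol rule passes | SAP rule passes |
|---|---|---|---|
| Intra-scanner | 80% | 0 / 0.2 / 1.8% | 0% |
| Intra-scanner | 85% | 31 / 61 / 89% | 3.3 / 3.2 / 2.8% |
| Intra-scanner | 86% | 66 / 86 / 97% | 18 / 15 / 13% |
| Intra-scanner | 90% | 100% | 99.9 / 99.7 / 98.7% |
| Inter-site | 80% | 0 / 0.2 / 3.5% | 0% |
| Inter-site | 85% | 19 / 37 / 65% | 4.1 / 3.9 / 3.5% |
| Inter-site | 90% | 99.2 / 99.9 / 100% | 95.5 / 94.9 / 93.8% |

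In the intra-scanner 85% row, true overall agreement is 86.3 / 87.1 / 88.1%. No trial of 48,000 passed the SAP rule and failed the protocol rule.

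**Sensitivity to the model.** A beta distribution that concentrates misses in fewer FOVs widens the gap (200 trials per setting, three-reader layout). With mean detection 0.90 and beta precision 0.5, mean overall agreement was 94.0% and mean a/N 87.0%; the protocol rule passed 100% and the SAP rule 27%. With mean detection 0.85 and precision 0.3, mean a/N was 81.8%; the protocol rule still passed 100% and the SAP rule 0%.

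**The case against.** **The SAP discloses the switch and its rule is stricter.** Following the SAP cannot inflate false success relative to the protocol, and nothing in the text permits a fallback. This stands, and it shows the SAP rule is deliberate. It does not correct the protocol, whose current text still states a different endpoint, estimator and pass rule. Protocol 11.3 says amendments are tracked in the revision history, and SAP section 1 says the two documents are to be read together.

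**Counting concordant misses is a legitimate precision measure.** The objective is repeatability and reproducibility, and a/N mixes detection with precision. That is a fair argument about which measure is better. It does not justify having two.

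**The regulator's formula and threshold cannot be seen.** SAP 3.1 says only positive agreement, which could mean a/N, a/(a+c) or APA. This stands and is why the source must be recorded. The 85% rule on a/N is nevertheless what SAP 6.4.1, 6.5.1 and 6.6.1 already state.

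**The worked example is extreme.** It has d/N = 342/3402 = 10.1%, whereas the logit-normal simulation at a/N = 85% implies 1.3 to 3.1%. Enrolment also requires a readily observable feature, and disqualifies a slide when the enrolling and verifying pathologists cannot agree on it. The example shows that the verdicts can split, not how often they will.

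**Timing cannot be judged.** Title and signature pages are not available, so no inference is drawn about when the SAP was fixed.

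**Conclusion.** The concern holds. The primary endpoint and pass rule of all three sub-studies contradict each other, and the plan is wrong as written until one is removed. The direction is certain, because it follows from d/N ≥ 0. The size is not, because neither document states an expected detection rate. Under the logit-normal model the conflict matters most when true a/N is near 85%, where the protocol rule passes 31 to 89% of intra-scanner trials and 19 to 65% of inter-site trials, against about 3% and 4% for the SAP rule. When d is near zero the two rules agree; when misses are concentrated in a subset of FOVs the gap is larger. The simulations resample whole FOVs and omit the extra resampling of readers in SAP 6.5.1; the ordering of the rules does not depend on that. This must be fixed before results are seen.

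**What to change.** Amend the protocol (synopsis, 3.2, 4, 8.1.2, 8.2 and 8.3) as follows.

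- Name positive agreement as the single primary endpoint of each sub-study, with the SAP's formula a/N and the 85% rule applied to its lower 95% limit.
- Keep overall agreement as a supportive estimate with no pass rule.
- Remove or rename the protocol's PPA, a/(a+c), and keep APA, 2a/(2a+b+c), under its own name, so that each term has one formula.
- Record the change in the revision history with the source of the 85% figure for positive agreement. If that source shows another formula or threshold, both documents must follow it.
- State when the endpoint was fixed relative to database lock.

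The cost is a protocol amendment, with the sponsor and investigator agreement and any IRB approval that protocol 11.3 requires. No new data or analyses are needed. The criterion will be harder to meet than the one the protocol now states.
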